5.3. Phase II

The Phase I part of the trial ended on May 30th, 2022 with the declaration of an RP2D of 100 mg/m²/week, and the study has already received a unanimous recommendation from an independent Data Safety Monitoring Board (DSMB) to continue the trial, moving to Phase II study.

The RP2D of 100 mg/m²/week, 3 of 4 weekly schedule, is justified based on safety, efficacy and pharmacokinetic considerations. The trend of dose-related neutropenia as the major safety feature points to the 100 mg/m²/week level as more tractable relative to 135 mg/m² (refer to full safety summaries in the IB). In terms of anti-tumor activity, the fact that, out of 6 evaluable, one confirmed RECIST partial response (despite one missed dose during the first two cycles) plus one highly prolonged stable disease were observed at 100 mg/m² as well as, out of 4 evaluable, 2 patients with substantial AFP reduction were observed points to reasonable activity at this dose level. Furthermore, pharmacokinetics at the 100 mg/m² dose level are in a meaningful range relative a continuous mouse tumor stabilization model predicting 0.2 uM average concentration threshold relative to the 100 mg/m² mean Cmax in HCC patients which is 7 fold higher at 1.35 uM and with AUC just slightly below the mouse threshold, 32.5 uM*h versus 35. Refer to IB for full PK descriptions. RECIST response and AFP reductions were observed at the 135 mg/m²/w level and PK was slightly higher but overall the anti-tumor pattern at 135 was similar to 100 mg/m². Therefore, overall, the 100 mg/m² level is justifiable as the RP2D.

In the Phase II portion, patients will receive the RP2D defined in the Phase I portion of the study as starting dose.

As soon as signs of toxicity are observed requiring a dose de-escalation, the dose will be decreased as described in Section 9.2.3.1, Table 6). A maximum of two dose decreases will be allowed, otherwise patient will have to be withdrawn from the study.

Patients will be enrolled in continuous, and continuously evaluated for endpoints, with a futility analysis and stopping criteria for unacceptable toxicity performed as described in Section 12. The enrollment will be stopped in the event of futility as described in Section 12, with no more than 20 subjects treated overall until non-futility can be declared, if appropriate. In any case, the Sponsor may stop or pause enrollments any time during the study based on safety, efficacy or strategic reasons.

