28 day follow up for laboratory abnormalities: in case hematology, blood chemistry, coagulation, study drug-related and clinically significant abnormalities persist beyond the 28-days follow up assessment, they should be followed until they resolve or the Investigator assess them as chronic or stable, or until alternative anticancer therapy is initiated. In this case, the reporting period will end at the time the new treatment is started.
28 days follow up for adverse events: the AEs reporting period ends 28 days after the last study treatment administration. The following events should be followed after the end of the reporting period: serious adverse events (SAEs) with outcome "not recovered" or "unknown" and study drug-related AEs with outcome "not recovered" or "unknown". They have to be followed until they resolve or the Investigator assess them as chronic or stable, or until alternative anticancer therapy is initiated. In this case, the reporting period will end at the time the new treatment is started.
* Cycle 1 Day 1 assessments: evaluations do not need to be repeated before study drug administration if they were performed at screening within 24 hours from treatment start.
° refer to Table 3

Table 3. Investigational Assessments details for Phase I

	Cycle 1 (Day)													Cycle 2 (Day)		
	D1, D15															
Timing related to EoI (hour)	Pre	-	0.0 [§]	0.15	0.30	1.0	2.0	4.0	6.0	7.0	8.0	24.0	48.0	72.0	168.0	Pre-dose
Study drug infusion		X														
PK blood sample ^a	X		X [§]	X	X	X	X	X		X	X	X	X	X	X	X
Blood pressure ^b	X [€]			X [€]										X ^{€#}	X [€]	

a. PK blood samples: all patients enrolled in the Phase I portion of the study will undergo blood draws for PK analysis (central laboratory).

Phase I Dose-Escalation

Cycle 1:

Day 1: before the start of infusion, 5 minutes before the end of infusion (0.0[§]), 15 minutes, 30 minutes, 1h, 2h, 4h, 6h, 8h after the end of study drug administration

Day 2: 24h after the end of study drug administration

Day 3: 48h after the end of study drug administration

Day 4: 72h after the end of study drug administration

Day 8: before the start of infusion

Day 15: before the start of infusion, 5 minutes before the end of infusion (0.0[§]), 15 minutes, 30 minutes, 1h, 2h, 4h, 6h, 8h after the end of study drug administration

Day 16: 24h after the end of study drug administration

Day 17: 48h after the end of study drug administration

Day 18: 72h after the end of study drug administration

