Day 22: 168h after the end of study drug administration

Cycle 2:

Day 1: before the start of infusion

Day 8: before the start of infusion

Day 15: before the start of infusion

Phase II

During the Phase II portion of the study, a sparse sampling procedure will be adopted.

b. Blood PressurePhase I Dose-Escalation*Cycle 1:*

Day 1: before the start of infusion and within 30 minutes after the end of study drug administration; before the blood sample for PK is taken.

Day 8: before the start of infusion and within 30 minutes after the end of study drug administration; before the blood sample for PK is taken.

Day 15: before the start of infusion and within 30 minutes after the end of study drug administration; before the blood sample for PK is taken.

Cycle 2:

Day 1: before the start of infusion and within 30 minutes after the end of study drug administration; before the blood sample for PK is taken.

Day 8: before the start of infusion and within 30 minutes after the end of study drug administration; before the blood sample for PK is taken.

Day 15: before the start of infusion and within 30 minutes after the end of study drug administration; before the blood sample for PK is taken.

+ before the treatment start and within 30 minutes after the end of infusion

§ 5 minutes before the end of infusion (EoI)

on D8 only

€ before the blood sample is taken

NMS-01940153E

Protocol for study MPSA-153-001 Version #5

MPSA-153-001_P5

09 January 2023

Table 4. Phase II Schedule of Events

Protocol activities and forms to be completed	Screening		Cycle 1 (day)				Cycle > 1 (day)				Last cycle	Off treatment assessments ²⁶		
	≤ 28	≤ 7	1	8	15	22	1	8	15	28		EoT ²⁵	28D FU	Bi- mth FU
Informed Consent ¹	X													
Relevant medical/oncologic history ²		X												
Physical examination and ECOG PS ³		X	X*				X				X		X	
Height	X													
Weight ⁴		X	X				X							
Temperature ⁵		X	X	X	X		X	X	X					
Blood pressure and heart rate ⁶		X	X	X	X		X	X	X		X		X	
Gastro-esophageal endoscopy ⁷		X												
12-lead ECG ⁸		X	X		X		As medically indicated				X			
Laboratory assessments														
Pregnancy test ⁹		X	X*				X				X			
Serology ¹⁰		X												
Hematology ¹¹		X	X*	X	X	X	X	X	X		X		X	
Blood chemistry ¹²		X	X*	X	X	X	X		X		X		X	
Coagulation ¹³		X	X*	X	X	X	X		X		X		X	
AFP ¹⁴		X							X*		X			
Urinalysis ¹⁵		X	As medically indicated				As medically indicated				X			
Other clinical assessments														
Concomitant medications ¹⁶	X	X	X				X				X		X	

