9.2. Treatment Administration

9.2.1. Treatment Dose and Schedule

NMS-01940153E will be administered IV for 3 consecutive weeks on days 1, 8, 15 followed by 1 week of rest, in a 28-day cycle. The total dose to be administered will be calculated based on patient's BSA (see Section 9.1.2). The duration of infusion will be dependent on the total dose to be administered:

- 1 hour infusion if ≤ 255 mg are administered
- 1 hour 30 minutes infusion if > 255 mg but < 375 mg are administered

The starting dose for the Phase I portion of the study is $100 \text{ mg/m}^2/\text{week}$, then according to the observed safety profile, dose increments of 25-35% will be applied until the MTD is reached. In presence of unacceptable toxicity observed at $100 \text{ mg/m}^2/\text{week}$, a lower dose level by 25-35% may be tested.

In the Phase II portion of the study, NMS-01940153E will be administered at the RP2D defined in the Phase I, as starting dose (see Section 5.2 for definitions).

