12.3.7.2. Pharmacokinetic

12.3.7.2.1. Phase I Dose Escalation

The pharmacokinetics of NMS-01940153E and its metabolite NMS-03593478 in plasma and urine will be assessed by standard non-compartmental analysis using Phoenix WinNonlin 8.1 or later version (Certara Company).

The following pharmacokinetic parameters will be provided on both Day 1 and Day 15: maximum concentration (C_{max}) and related time of achievement (T_{max}), last detectable concentration (C_{last}) and related time of observation (T_{last}), area under concentration versus time up to 168 hours (dosing interval), half-life of the terminal phase ($t_{1/2,z}$), plasma clearance (CL), volume of distribution (Vss) and renal clearance (CLR).

On Day 1, for NMS-01940153E and NMS-03593478, maximum concentration, $C_{max,D1}$, and related time of achievement, $T_{max,D1}$, last detectable concentration, $C_{last,D1}$, and related time of observation, $T_{last,D1}$, will be taken directly from the raw data.

Area under concentration versus time up to the last detectable concentration (AUClast) will be calculated using the linear trapezoidal rule. The half-life of the terminal phase, $t_{1/2,z}$, will be determined by linear regression analysis of the natural-log concentration versus time curve according to the formula:

$$t_{1/2,z} = \frac{\ln(2)}{\lambda_z}$$

where λ_z is the slope of the regression line. A minimum of three data points will be used in calculating λ_z .

$AUC_{\infty}(D1)$ will be calculated by adding the portion of the area calculated as $C_{last,D1}/\lambda_z$ to AUClast,D1.

The clearance (CL) of NMS-01940153E will be calculated according to the formula:

$$CL = \frac{\text{Dose}}{\text{AUC}_{\infty_{D1}}}$$

The volume of distribution at steady state (V_{ss}) of NMS-01940153E will be calculated according to the formula:

$$V_{ss} = CL \cdot MRT, \text{ where } MRT = \frac{AUMC_{D1}}{AUC_{D1}} - \frac{t_{inf}}{2}$$

On Day 15, C_{max,D15}, T_{max,D15}, Clast,D15 and Tlast,D15 will be taken directly from the raw data.

AUC_{0-168,D15}, AUClast,D15 and AUCD15 will be calculated as on Day 1.

The clearance (CL) of NMS-01940153E will be calculated according to the formula:

$$CL = \frac{\text{Dose}}{\text{AUC}_{\tau, D15}}$$

where AUC τ is the area under the curve in the dosing interval.

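### Phase I plasma AUC uses the linear trapezoidal rule across a gap of about 95 h on a falling curve, which biases parent-drug AUC up and clearance down by single-digit percentages

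*Protocol*

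**What the plan says.** Protocol section 12.3.7.2.1 plans a non-compartmental analysis of the Phase I plasma data. On the integration rule it says: "Area under concentration versus time up to the last detectable concentration (AUClast) will be calculated using the linear trapezoidal rule". The Day 15 areas "will be calculated as on Day 1", so the rule is linear on both days. No log-down rule is given for the declining part of the curve.

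The terminal slope comes from a regression of log concentration on time. On Day 1, AUC to infinity is AUClast plus the last concentration divided by that slope, and CL is dose over AUC to infinity. On Day 15, CL is dose over the AUC of the dosing interval. Vss is CL times MRT, and MRT uses AUMC, for which no integration rule is stated.

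The sampling times are in section 7 (Table 3, footnote a) and section 11.6.1 (Table 13). After 8 h they are:

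- Day 1 profile: 24 h and 48 h, then "Day 4: 72h after the end of study drug administration", then "Day 8: before the start of infusion".
- Day 15 profile: 24 h and 48 h, then "Day 18: 72h after the end of study drug administration", then "Day 22: 168h after the end of study drug administration".

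Section 5.3 cites a Phase I exposure in support of the Phase II dose: a mean Cmax of 1.35 uM, "with AUC just slightly below the mouse threshold, 32.5 uM*h versus 35". SAP section 2 leaves the PK analysis to a separate document, which is not among those supplied.

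**The concern.** Once the infusion ends, the parent-drug concentration falls. The linear rule joins neighbouring samples by a straight line, which lies above a convex falling curve. The excess grows with the number of half-lives between samples, so the step after 72 h is the most exposed. The error is systematic, and more patients do not reduce it.

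AUC and CL are named Phase I outputs under a secondary endpoint, and both inherit the bias. Vss inherits it through CL, and also through MRT if AUMC is integrated linearly. The AUC set against the 35 uM*h threshold would be affected too if it was obtained with this rule.

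**Working it through.** There is no stated figure to reproduce, because the documents do not quantify the integration error. The check therefore estimates its size.

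**Inputs from the Protocol.** Linear rule on both days (12.3.7.2.1). Sampling times (section 7 and Table 13). Infusion time: "1 hour infusion if ≤ 255 mg are administered" (9.2.1). Cmax 1.35 uM and AUC 32.5 uM*h at 100 mg/m² (5.3).

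**Assumptions.** No half-life is given, so the terminal half-life is varied from 18 to 96 h and the distribution half-life from 0.5 to 4 h. A terminal half-life of 12 h cannot match both Cmax 1.35 and AUC 32.5 in this model.

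**Step 1: the gap.** Day 15: 168 - 72 = 96 h. On Day 1 the last sample is about 168 h after the start of the infusion, hence 167 h after the end of a 1 h infusion: 167 - 72 = 95 h.

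**Step 2: one log-linear segment.** With slope λ and gap Δ, the linear area is Δ(C1 + C2)/2 and the true area is (C1 - C2)/λ. Their ratio is (x/2)·coth(x/2), where x = ln2·Δ/half-life. For a 24 h half-life and Δ = 96 h, x/2 = 0.693 × 96/24/2 = 1.386 and coth(1.386) = 1.133. The ratio is 1.57, an overstatement of 57%. The other half-lives, for the last segment alone:

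| Terminal half-life | 18 h | 24 h | 36 h | 48 h | 72 h | 96 h |
|---|---|---|---|---|---|---|
| Excess | 94% | 57% | 27% | 15.5% | 7% | 4% |

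**Step 3: the whole profile.** The last segment is only part of the total (about 10 to 11% of AUC0-168 at a 24 h half-life), so the effect on total AUC is much smaller. A noiseless two-compartment curve with a 1 h infusion was scaled to Cmax 1.35 uM and AUC 32.5 uM*h, sampled at the Day 1 times and compared with the exact integral. The terminal slope came from the last three points. Ranges run over the distribution half-lives.

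| Terminal half-life | AUC to infinity, linear rule | CL, linear rule |
|---|---|---|
| 24 h | +8.2 to +9.0% | -7.6 to -8.2% |
| 36 h | +6.0 to +7.6% | -5.7 to -7.0% |
| 48 h | +4.1 to +6.2% | -3.9 to -5.8% |
| 96 h | +1.0 to +4.1% | -1.0 to -3.9% |

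Over 18 to 96 h, AUC0-168 is overstated by 1.4 to 9.0%, AUC to infinity by 1.0 to 9.0%, and CL is understated by 1.0 to 8.3%. The long gap contributes 1.2 to 6.4 percentage points of AUC0-168. Most of the rest comes from the earlier declining segments. The short rise during infusion pulls slightly the other way and is included.

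**Step 4: the alternative.** Linear-up/log-down on the same samples gives -0.3 to +2.4% on AUC0-168 and -0.2 to +1.8% on AUC to infinity.

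**Step 5: if 168 h is below detection.** AUClast then stops at 72 h or earlier, and only gaps of 24 h or less remain. The linear error on the 0-72 h area is about -0.3 to +6%.

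**Step 6: Vss.** If AUMC is also linear, Vss is understated by about 3 to 14%, against about 0 to 3% with log-down.

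**Step 7: the 32.5 uM*h figure.** The stated shortfall is 1 - 32.5/35 = 7.1%. If 32.5 came from the linear rule, the corrected value lies between 32.5/1.09 = 29.8 and 32.5/1.01 = 32.2. The shortfall would be between 1 - 32.2/35 = 8% and 1 - 29.8/35 = 15%.

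**The case against.** The linear rule is a recognised non-compartmental option and nothing in the Protocol contradicts it. The log-linear fit is used only for the terminal phase. This stands: the point is a choice of method that suits this sampling grid poorly, not an internal contradiction.

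The planned inferences are hardly touched. With linear superposition at the Table 13 times, the Day 15/Day 1 ratio of AUC0-168 shifts by less than 1% for half-lives of 18 to 96 h. A roughly proportional bias should also cancel in the dose-proportionality slope, though that was not simulated. Renal clearance uses AUC0-72 and avoids the long gap. Phase II uses mixed-effect modelling, which needs no trapezoids. All of this stands, but absolute AUC, CL and Vss are still biased.

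A reader might infer that the exposure argument for the Phase II dose fails, or that the bias equals the 7% shortfall. The documents do not support either reading. They do not say which AUC, which day or which rule produced 32.5, or how 35 was obtained. A bias near 7% or more needs the shorter assumed half-lives. The threshold is itself approximate: it is described as a 0.2 uM average, and 0.2 × 168 = 33.6 if the interval is 168 h (an assumption), not 35. The AUC is already reported as below the threshold and stays below it after correction. Section 5.3 also relies on safety, response, AFP and Cmax, and no decision rule uses 35.

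The separate PK document may refine the rule. If it does, the Protocol's explicit sentence should be brought into line with it.

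Finally, Phase I ended in May 2022, so a change now follows the data. That calls for open labelling and for showing both sets of results.

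**Conclusion.** The point holds as a minor methods improvement. As written, the rule overstates parent-drug AUC0-168 and AUC to infinity by about 1 to 9% and understates CL by about 1 to 8%, if the terminal half-life is between 18 and 96 h and the drug is detectable at 168 h. The direction was the same in every feasible scenario, but the size depends on a half-life that the documents do not give. If the drug is undetectable at 168 h, only the smaller error on the 0-72 h area applies. For the metabolite, which first rises, the direction is less certain.

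The 57% figure for the last segment at a 24 h half-life should not be read as the error in AUC. No sample size, error rate, MTD rule or stopping rule is affected.

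**What to change.** In section 12.3.7.2.1, specify the linear-up/log-down trapezoidal rule for plasma AUC and AUMC on Day 1 and Day 15, and align the separate PK document. Re-derive Phase I AUC, CL and Vss with it. Report the linear results alongside, and state that the change was made after the Phase I data were available.

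State which AUC, day and rule produced the 32.5 uM*h in section 5.3. If it came from the linear rule, restate the value and revise the description of how close it lies to 35.

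The cost is one software setting, one or two sentences and a rerun on existing data, with no new samples or patients. The downside is that reported AUC becomes a few percent lower.

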Accumulation ratios for NMS-01940153E and NMS-03593478, based on C_{max} (R_A, C_{max}) and AUC_{last} (R_A, AUC_{last}) will be calculated as the ratio between the individual parameter obtained on Day 15 to the corresponding one on Day 1.

On Day 1 and Day 15, metabolite to parent ratio will be calculated based on C_{max} and AUC_{last} values.

On Day 1 and Day 15, the amount of NMS-01940153E and its metabolite NMS-03593478 excreted in urine in the time interval 0-72 h (Ae₀₋₇₂) will be calculated multiplying the urinary concentration by the urinary volume in the collection times: 0-6, 6-24, 24-48 and 48-72 hours. The parameter will be also expressed as percent of dose (fe%). For the metabolite, the parameter expressed as percent of dose will be calculated after correction of the dose for the molecular weight of the compound.

Renal clearance of NMS-01940153E and its metabolite NMS-03593478 will be calculated as:

$$CLR = Ae_{0-72} / \text{AUC}_{0-72}$$

Statistical analysis

Descriptive statistics (mean \pm SD, CV%, min, max, median) will be calculated for plasma and urine concentration data and pharmacokinetic parameters.

Statistical analysis will be performed after a log-transformation of the data of NMS-01940153E treatment. For each group separately, a mixed effect model will be fitted with day

as fixed effect and subject as a random effect. Day 15 will be compared to Day 1 for each dose level. The ratio will be calculated by back-transforming the difference between the Least Square means. Using the estimate of variance, 90 % confidence intervals will be calculated for the difference and back-transformed. Results of the analyses will be reported in the paragraph of the statistical results.

The power method will be used to evaluate the dose proportionality of NMS-01940153E and possibly its metabolite. C_{\max} , AUC_{last} , AUC_{0-168} and AUC data on Day 1 and Day 15. Dose *versus* C_{\max} and AUC s relationship will be performed using the power model

$$y = a \cdot \text{Dose}^b$$

This relationship becomes linear after a logarithmic transformation

$$\log(y) = \log(a) + b \cdot \log(\text{dose})$$

where a is the intercept to y (AUC) axis and b is the slope of the regression line. Dose proportionality required slope to be close to unity for dose dependent parameters, and decision on dose proportionality will be made based on the inclusion of the theoretical slope of 1 in the 90 % confidence intervals.

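### The Phase I metabolite/parent and accumulation ratios use AUClast, whose end time can differ between analytes or days; AUC0-168, already planned, would give a fixed window

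*Protocol*

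**What the plan says.** All of the relevant text is in Protocol section 12.3.7.2.1.

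- **Metabolite/parent ratio.** "On Day 1 and Day 15, metabolite to parent ratio will be calculated based on" Cmax and AUClast.
- **Accumulation.** For parent and metabolite, the ratios based on Cmax and AUClast "will be calculated as the ratio between the individual parameter obtained on Day 15 to the corresponding one on Day 1".
- **AUClast.** "Area under concentration versus time up to the last detectable concentration (AUClast) will be calculated using the linear trapezoidal rule". Tlast is read from the raw data, so the end time depends on what the assay detects.
- **Fixed-window area.** The parameter list for Day 1 and Day 15 includes "area under concentration versus time up to 168 hours (dosing interval"). It is an input to the dose-proportionality model but to neither ratio.
- **Unequal end times.** No rule says what to do when Tlast differs between analytes or between days.

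Table 13 gives both analytes the same samples. After the Day 1 dose, the samples at 72 h and earlier are followed only by the Day 8 pre-dose sample, about 168 h after the start of infusion. After the Day 15 dose, the 72-h sample is followed only by one at 168 h after the end of infusion. SAP section 2 leaves pharmacokinetic analysis to a separate document, which is not available here.

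**The concern.** A ratio of two exposures is interpretable only if both cover the same time span. AUClast does not guarantee this, because assay sensitivity at one late sample sets its end point. With nothing sampled between 72 h and 168 h, losing that sample removes 168 − 72 = 96 of 168 hours at a stroke. A metabolite that falls below the limit before the parent makes the metabolite/parent ratio read low. A Day 1 profile that ends early while Day 15 does not makes accumulation read high. Neither reflects a change in pharmacokinetics.

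The same section matches windows elsewhere: Day 15 clearance uses the area over the dosing interval, and renal clearance divides urinary recovery over 0-72 h by AUC0-72. Only the two AUC ratios lack a fixed window. Phase I expects 12 to 15 treated patients in cohorts of 3 to 6 (Protocol section 12.1), so one or two affected patients can move a dose-level summary.

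**Working it through.** The plan gives no figure to reproduce. The check asks when the windows diverge and by how much the ratios then move.

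**Step 1. All samples quantifiable.** Both analytes end at the same sample on each day. The last Day 1 sample is at about 168 h from the start of infusion, the last Day 15 sample at about 169 to 169.5 h. The gap is 1 to 1.5 h, and 1.5/168 = 0.9%. The AUClast ratios are then practically AUC0-168 ratios.

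**Step 2. Metabolite lost at 168 h, parent detected.** The documents give no half-lives and no quantification limit. Assume mono-exponential decline with half-life 16.7 to 60 h. The lower end is what a single exponential implies for the parent from the Cmax of 1.35 µM and AUC of 32.5 µM·h in Protocol section 5.3: ln 2 × 32.5/1.35 = 16.7 h. The upper end is a free assumption. With k = ln 2/half-life, the share of total area reached by time t is f(t) = 1 − exp(−kt). The parent area is unaffected, so the reported ratio divided by the 168-h ratio is f(72)/f(168) for the metabolite.

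| Half-life (h) | f(72) | f(168) | f(72)/f(168) | Ratio too low by |
|---|---|---|---|---|
| 16.7 | 0.950 | 0.999 | 0.95 | 5% |
| 24 | 0.875 | 0.992 | 0.88 | 12% |
| 40 | 0.713 | 0.946 | 0.75 | 25% |
| 60 | 0.565 | 0.856 | 0.66 | 34% |

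**Step 3. The nominal sampling times with the linear trapezoid.** This illustration used a two-exponential parent scaled to the same Cmax and AUC, a first-order metabolite with a true AUC ratio of 0.1, equal terminal half-lives of 20 to 60 h for both analytes, and limits of 0.5 to 20 nM. All but the scaling is assumed.

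- Limit 2 nM or below and half-life 30 h or more: AUClast and full-interval ratios agree to within 0.002.
- Half-life 20 h, limit 2 nM; metabolite ends at about 73 h from the start of infusion, parent reaches 168 h: Day 1 ratio 0.064 against 0.098, or 35% low (1 − 0.064/0.098).
- Half-life 30 h, limit 10 nM, same pattern: 0.047 against 0.088, or 47% low.
- Half-life 45 h, limit 10 nM; metabolite lost on Day 1 only: Day 1 ratio 0.030 against 0.074, or 59% low, and metabolite accumulation 3.40 against 1.36.
- Parent accumulation: never off by more than 0.003.

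The effects exceed those in step 2 because the metabolite forms gradually, which places more of its area late, and the linear rule overstates the area across the 96-h gap.

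**Step 4. Accumulation in the mono-exponential model.** If Day 1 ends at 72 h and Day 15 at 168 h, the ratio reads 1.05, 1.14, 1.40 and 1.77 at the four half-lives. The true value, 1 + exp(−168k) + exp(−336k), is 1.00, 1.01, 1.06 and 1.16. The 168-h concentration rises from Day 1 to Day 15 by that same factor, so the assay limit must fall inside a gap of about 0.1%, 0.8%, 6% or 16% for this to happen.

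**The case against.** The strongest reply is that the documents show a possibility, not an occurrence. Both analytes share one schedule that reaches about 168 h, and no Tlast data, quantification limit, half-life or metabolite level is given. This stands: a reader might infer that the end times do differ, and the documents do not support that.

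A reader might also infer that parent accumulation is badly inflated. Step 4 shows the narrow condition required. Scaling a mono-exponential to the AUC of 32.5 µM·h gives parent concentrations at 168 h of about 1.3, 7, 31 and 54 nM at half-lives of 16.7, 24, 40 and 60 h. The large parent effects therefore need a limit of roughly 30 to 54 nM. This part of the objection also stands.

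A third tempting reading is that the dose-proportionality decision is compromised. If one third of patients at 100 mg/m² and none at 135 lost the 168-h point, the AUClast slope would shift by (1/3) × ln(f(168)/f(72))/ln(1.35), which is 0.06 to 0.46. That loss pattern is invented. The power model is already planned on AUC0-168 and AUC as well as AUClast. With an assumed 6 patients per level and 30% CV, the 90% interval for the slope has a half-width of about 1.0.

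The sponsor can add that Tlast and AUC0-168 are reported anyway, so a reader can detect a mismatch, and that the separate pharmacokinetic document may contain a rule. Both are fair. Even so, the protocol names AUClast for these ratios, and that document would have to depart from it.

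**Conclusion.** The point holds as a cheap improvement. The stated rule permits ratios over unequal windows although a fixed-window area is already planned. The effect is nil when all 168-h samples are quantifiable. If the metabolite alone is lost at 168 h, the metabolite/parent AUC ratio is about 5% to 34% too low under mono-exponential decline with half-lives of 17 to 60 h. It can be lower still under the gradual-formation model of step 3. These sizes rest on assumptions that the documents neither confirm nor exclude.

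The consequence is limited to descriptive secondary Phase I pharmacokinetics. No stated rule for dose-limiting toxicity, MTD, Phase II response, futility or sample size uses these ratios. Phase I ended on 30 May 2022, before this protocol version of 9 January 2023, so only analysis and reporting are affected.

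**What to change.** In section 12.3.7.2.1 and the separate pharmacokinetic plan:

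1. Compute the metabolite/parent and accumulation ratios from AUC0-168 on both days. State its Day 1 calculation, which the section does not spell out.
2. Where the 168-h value is undetectable for either analyte or either day, choose one of two rules in advance. Either use a common observed window for numerator and denominator, for example AUC0-72, already needed for renal clearance; or complete the tail with lambda-z by the same method in both. Flag these patients.
3. Do not mix tail methods within a ratio. On the same mono-exponential curve, a linear trapezoid across 72 to 168 h and an exponential tail give AUC0-168 values that differ by 3% to 7%.
4. Do not pool 72-h ratios unmarked with 168-h ratios. In the step 3 illustration with half-life 20 h and limit 5 nM, both analytes end at about 73 h, and the Day 1 ratio is 0.073 against 0.098 over the full interval.
5. Keep AUClast as a descriptive value shown with Tlast, and read dose proportionality from the AUC0-168 model already planned.

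The cost is a few sentences and no new samples. The downside is a flagged extrapolated or shortened window in the affected patients.
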